3.2.3 SWOT analysis

STRENGHTS	WEAKNESS
 Possibility to improve patient's outcome and reduce hospital costs Low cost of the new treatment 	 High number of patients to be recruited Variability of the techniques
OPPORTUNITIES	THREATS
 Applicable to a relevant proportion of patients affected by grade III hemorrhoids. Reduce time of the operation Reduce hospital costs Improvement of the patients QoL 	- Common risks of all surgical procedures used for hemorrhoids

3.3 Randomization

Written informed consent will be obtained prior to surgery by the operating surgeon. Computergenerated randomization will be used to create an allocation sequence to assign patients to the different study arms. Randomization will be computer generated and centrally controlled by an operator not involved in the study.

3.4. Subject Recruitment and Screening

Each patient with grade III hemorrhoids eligible for the inclusion and exclusion criteria will be randomized after obtaining written informed consent about the study. Patients will be given information about the risks, discomforts, and potential benefits of both treatments. The randomization protocol will be explained to the patient before consent is obtained.

3.5 Participating Institution and Surgeons

This multicenter trial is opened to the contribution of surgeons across Europe in order to achieve the required number of patient recruitment in the shortest period.

- All surgeons must have prior experience in the treatment of hemorrhoids with DGHAL and mucopexy.
- All participating institutions must have IRB (Institutional Review Board)/Ethics Committee approval in order to enroll patients in the trial.
- Recruitment of Centers will be by direct invitation or spontaneous proposal of Coloproctology Units interested in the study.
- Surgeons involved MUST have no potential conflict of interests in the procedure

3.6 Definition of Outcome Measures

Please use the following definitions:

- duration of the hospital stays (defined as from beginning of surgery to time of discharge, measured in hours)
- questionnaires administered to patients at 1 week, 4 weeks and 1 year follow-up
- Recurrence is defined as persistent or recurrent hemorrhoid symptoms including prolapse,
 proctorragia, hemorrhoidal thrombosis
- Hemorrhoidal prolapse is defined as III degree if the prolapse needs to be repositioned into the anal canal manually and of II degree if it returns spontaneously into the anal canal.

- Hemorrhoid engorgement visible only at control anoscopy but without symptoms will not be considered as Hemorrhoidal prolapse
- Proctorrhagia will be defined as minor if traces of blood can be detected at defecation, moderate if there is occasional bleeding at defecation, severe if bleeding occur after any defecation

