3.2.1 Primary

[figure not shown]
Primary aim of the Hamlet trial is to demonstrate that mucopexy without DGHAL for grade III haemorrhoids have equivalent recurrence rate at 1 year follow up of DGHAL with mucopexy procedure

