3.2.2 Secondary

- SAFETY: Demonstration that the new treatment will not add related morbidity
- Comparison of the outcome among the two devices (THD and AMI/ HAL-RAR) for DGHAL

_

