4 STUDY INTERVENTION

4.1 Preoperative work-up

All the patients will have full proctological examination including anoscopy. Those with familiarity for colorectal cancer and those over 50 will be invited to have screening colonoscopy to exclude other sources of bleeding

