5. STATISTICAL ANALYSIS

5.1 Sample Size Determination:

A sample size calculation shows that 100 subjects per arm will suffice for accepting of the equivalent hypothesis with power of 0.8 and a type I error probability of 0.05, an equivalent limit of 15% and expected percentage of success in both control and experimental group of 90% (sample size calculated with R).

5.2 Statistical Methods:

Results will be expressed as either mean and standard deviation (SD) or frequency (percentage). Between-group comparisons will be performed using Student's t-test (normally distributed data) or Mann-WhitneyU test (skew data) for continuous variables or Chi-square test for categorical variables. All hypotheses will two-tails with p < 0.05 considered as statistically significant.

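### The questionnaires start only after surgery, so within-patient change cannot be described and follow-up scores cannot be baseline-adjusted

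*Protocol*

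**What the plan says.** Section 3.6 (Definition of Outcome Measures) includes "questionnaires administered to patients at 1 week, 4 weeks and 1 year follow-up". It does not name the instruments or say what they measure.

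Section 4.1 describes the work-up before surgery: "All the patients will have full proctological examination including anoscopy", plus an invitation to colonoscopy for some patients. It mentions no questionnaire, and no other section adds one before surgery.

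The primary aim in section 3.2.1 is that mucopexy alone should "have equivalent recurrence rate at 1 year follow up of DGHAL with mucopexy procedure". Section 3.2.2 has two secondary items: "SAFETY: Demonstration that the new treatment will not add related morbidity" and "Comparison of the outcome among the two devices (THD and AMI/ HAL-RAR) for DGHAL". Quality of life appears as a possible gain only in the SWOT table of section 3.2.3, under opportunities: "Improvement of the patients QoL".

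Section 5.2 plans between-group tests: Student's t-test or "Mann-WhitneyU test (skew data) for continuous variables", and chi-square for categorical ones. It plans no analysis of change from baseline.

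**The concern.** Section 1.1 presents treatment as a means of relieving symptoms, and section 3.2.3 hopes for better quality of life. Both are changes from the state before surgery, and the questionnaire schedule does not record that state. A score at 1 year can be compared between arms, but nobody can say from it how far a patient has moved.

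The second loss is precision. A score taken before surgery is often among the better predictors of the same score afterwards, and adjusting for it removes part of the between-patient variation. Without it, that option is closed.

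The timing matters because the omission cannot be repaired. An analysis plan may choose the model later, but once a patient has been operated on the preoperative score is gone. This is therefore a point about what the protocol schedules, not about detail that may be left to an analysis plan.

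**Working it through.** **1. Is there a baseline anywhere?** The time points in 3.6 are 1 week, 4 weeks and 1 year. The preoperative content in 4.1 is an examination with anoscopy and, for some, a colonoscopy invitation. Sections 3.3 and 3.4 place consent before randomisation and surgery but attach no form to it. There is no baseline questionnaire.

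**2. Does the plan's own sample size depend on it?** Section 5.1 states that "100 subjects per arm will suffice for accepting of the equivalent hypothesis with power of 0.8", with type I error 0.05, a limit of 15% and 90% success in both arms. This is a calculation for a binary outcome:

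- Two one-sided tests, n = 2 × 0.9 × 0.1 × (z for 1 − α + z for 0.90)² / 0.15². At one-sided 0.05: 0.18 × (1.645 + 1.282)² / 0.0225 = 68.5, so 69 per arm. At one-sided 0.025: 84.1, so 85. With a continuity correction the latter becomes 97.
- The ordinary two-sided 0.05 formula for 90% against 75% with 80% power gives exactly 100.

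The protocol does not say which formula was used; that is a separate matter. None of these formulas contains a questionnaire score, so the figure of 100 neither supports nor weakens this point.

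**3. What would a baseline be worth for a questionnaire score?** Inputs: 100 per arm (5.1), two-sided 0.05 (5.2), and 80% power borrowed from 5.1. The correlation r between baseline and follow-up is not in the documents, so it is an assumption, shown over a range. The score is assumed to be roughly continuous and to be the same instrument at both times.

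- Variance of the arm difference relative to follow-up scores alone: 1 − r² with baseline adjustment (ANCOVA, large samples); 2(1 − r) with change scores.
- Equivalent sample size per arm under adjustment: 100 / (1 − r²).
- Detectable difference in SD units: (1.960 + 0.842) × √(2(1 − r²)/100). With r = 0 this is 2.802 × 0.1414 = 0.396.
- Power for 0.4 SD: Φ(0.4 / √(2(1 − r²)/100) − 1.960). With r = 0 this is Φ(2.828 − 1.960) = Φ(0.868) = 0.81.

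| Assumed r | ANCOVA variance factor | Equivalent n per arm | Detectable difference (SD) | Power for 0.4 SD | Change-score variance factor |
|---|---|---|---|---|---|
| No adjustment | 1.00 | 100 | 0.40 | 81% | – |
| 0.2 | 0.96 | 104 | 0.39 | 82% | 1.6 |
| 0.3 | 0.91 | 110 | 0.38 | 84% | 1.4 |
| 0.4 | 0.84 | 119 | 0.36 | 87% | 1.2 |
| 0.5 | 0.75 | 133 | 0.34 | 90% | 1.0 |
| 0.6 | 0.64 | 156 | 0.32 | 94% | 0.8 |
| 0.7 | 0.51 | 196 | 0.28 | 98% | 0.6 |

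For r of 0.3 to 0.6, adjustment cuts the variance by 9% to 36%. The last column shows that change scores are less precise than raw follow-up scores when r is below 0.5, so the gain comes from adjustment, not from subtracting the baseline.

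**The case against.** The strongest reply is that nothing the trial sets out to prove needs this baseline. The primary endpoint is recurrence, the secondary items are morbidity and a device comparison, and the planned tests compare groups. The questionnaires are unnamed and could be pain, recovery or satisfaction forms, some of which have no meaning before surgery. The correlation may also be low: entry is restricted to symptomatic grade III disease and 90% success is expected, so scores may vary little beforehand and cluster near the best value afterwards. At r = 0.3 the detectable difference falls only from 0.40 to 0.38 SD.

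Most of this stands and sets the limits of the point. Four stronger readings are tempting, and the document does not support them:

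- *That a quality-of-life endpoint has been made unmeasurable.* Quality of life is a SWOT entry, not an endpoint, and a difference between arms at follow-up could still be estimated if one of the questionnaires measures it.
- *That the comparison is biased because simple randomisation may leave the arms unequal at the start.* Chance imbalance is already allowed for in the error rate of the test. Only precision suffers.
- *That recurrence needs a baseline questionnaire because its definition includes persistent symptoms.* Section 3.6 counts persistent and recurrent symptoms alike as failure, so the two need not be separated. Nor does the protocol say that the questionnaire decides recurrence.
- *That comparing raw scores is the least precise choice.* Change scores are worse when r is below 0.5.

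A fair reply is also that the choice of an adjusted model may be left to an analysis plan. It may, but the collection of the baseline may not.

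**Conclusion.** The point holds as a minor design gap. As scheduled, the questionnaires cannot describe within-patient change, cannot be baseline-adjusted, and cannot by themselves document the improvement named in section 3.2.3. The follow-up comparison between arms remains unbiased, and the recurrence endpoint and its 100 per arm do not change.

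The size depends on an assumed correlation. At 0.3 to 0.6, adjustment would make 100 per arm act like 110 to 156 for these outcomes; at 0.2 it would be worth only about 4 patients per arm. This assumes an instrument with a meaningful preoperative value and a roughly continuous score, which the protocol does not establish.

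**What to change.** In section 3.6, name the questionnaires. For each symptom or quality-of-life instrument that has a meaningful preoperative value, set the schedule to baseline (after consent, before allocation is known), 1 week, 4 weeks and 1 year, using the same instrument each time. In section 5.2 or the analysis plan, state that arms are compared on those scores at each follow-up by ANCOVA adjusted for baseline, with estimates and 95% confidence intervals.

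The cost is one extra form per patient at a preoperative contact that already takes place, and a line or two of text. The sample size does not change. Instruments without a preoperative value, such as satisfaction forms, gain nothing and should stay as scheduled. For patients already operated on, the baseline cannot be recovered. If it is not added, any quality-of-life statement should be confined to differences between arms at follow-up.

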3. STUDY DESIGN

3.1 General Design

Prospective, multi-centre, parallel-arm randomized controlled equivalence trial. Eligible patients will be randomized to either mucopexy without Doppler guided artery ligation or mucopexy with doppler guided hemorroidal artery ligation.

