3.7.2 Exclusion Criteria

- Any previous hemorrhoid surgery
- Participants expressing clear preference for one of the interventions
- Pregnancy
- Inability to understand the informed consent
- Oral anticoagulants of congenital defects of the coagulation
- Patients with immunodepression (i.e. HIV)
- Other proctological diseases (fissures, fistulas, condyloma, etc)
- IBD involving the anus ore the rectum

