4.3 Post-Operative Management

Postoperative care will be according to current standards as directed by the operative surgeon.

- Pain control will initially be provided using parenteral (intramuscular, intravenous or epidural) administration of narcotics or analgesics.
- bulking agents (psyllium) or osmotic laxatives will be prescribed in order to allow easy defecation

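### The primary endpoint rests on symptoms known mainly from the patient, and the protocol body specifies no masking of the patient or of whoever records recurrence

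*Protocol*

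**What the plan says.** Protocol 3.2.1 sets the primary aim: mucopexy alone should "have equivalent recurrence rate at 1 year follow up of DGHAL with mucopexy procedure". Section 3.6 gives the definition: "Recurrence is defined as persistent or recurrent hemorrhoid symptoms including prolapse", together with bleeding and haemorrhoidal thrombosis. Bleeding is graded by how much and how often blood appears at defecation, and prolapse by whether it has to be pushed back by hand. An examination finding without symptoms does not establish prolapse: "Hemorrhoid engorgement visible only at control anoscopy but without symptoms will not be considered as Hemorrhoidal prolapse". In a separate bullet, the same section lists "questionnaires administered to patients at 1 week, 4 weeks and 1 year follow-up".

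On design, section 3.1 says "Prospective, multi-centre, parallel-arm randomized controlled equivalence trial" and does not mention masking. Section 3.3 says "Randomization will be computer generated and centrally controlled by an operator not involved in the study", which concerns how the sequence is produced and held. Section 3.7.2 excludes "Participants expressing clear preference for one of the interventions". No section of the protocol body names the person who determines recurrence, or says whether that person or the patient knows the allocation.

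**The concern.** Central randomization protects the assignment before it is made. It does not protect what is reported in the following year. Whether there were traces of blood, or whether a prolapse went back unaided, is a matter of recall and judgement. A patient who knows that the Doppler device was or was not used may answer differently, and so may an interviewer who knows.

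In an equivalence trial this can work both ways. A spurious difference can hide true equivalence, and a reporting difference that offsets a real one can produce a false claim of equivalence. Intention-to-treat analysis (5.3) keeps patients in their allocated arms but does not correct an outcome that was measured differently in the two arms. Masking has to be settled before the first patient consents, so it cannot be left to a later analysis plan.

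**Working it through.** **Inputs from the Protocol, 5.1.** 100 per arm, equivalence limit 15 points, expected success 90% in both arms (recurrence 10%), power 0.80, type I error 0.05.

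**The plan's own figure.** For equivalence by two one-sided tests with equal true rates, n per arm = 2p(1−p)(z₁₋α + z₁₋β/₂)²/Δ².

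- One-sided α = 0.05: 2 × 0.9 × 0.1 × (1.645 + 1.282)²/0.15² = 68.5, so 69.
- One-sided α = 0.025: 2 × 0.9 × 0.1 × (1.960 + 1.282)²/0.15² = 84.1, so 85.

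The stated 100 is not reproduced by this formula, but it exceeds both results. The planned size is therefore not too small on these inputs. The rest of the check uses 100 per arm as planned.

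**Decision rule assumed.** Equivalence is declared if the 90% Wald interval for the difference lies wholly within ±15 points (one-sided 0.05). The protocol does not state this rule, so results for one-sided 0.025 (95% interval) are given as well. The probabilities come from exact enumeration of all pairs of binomial outcomes.

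**Reporting shifts assumed.** The protocol gives none. The values used are a spurious excess of 3 or 5 points, and 10% or 20% of recurrences in the mucopexy arm going unreported. When true recurrence in that arm is 25%, the reported rates are 25 × 0.9 = 22.5% and 25 × 0.8 = 20%.

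**Hand check without bias.** SE = √(2 × 0.1 × 0.9/100) = 0.0424. Then 0.15/0.0424 − 1.645 = 1.89, and 2Φ(1.89) − 1 = 0.94, in agreement with the enumeration.

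| Truth | Reported recurrence | Equivalence declared, one-sided 0.05 | One-sided 0.025 |
|---|---|---|---|
| 10% vs 10% | 10% vs 10% | 93.8% | 88.0% |
| 10% vs 10% | 10% vs 13% | 83.7% | 74.0% |
| 10% vs 10% | 10% vs 15% | 69.3% | 57.2% |
| 10% vs 25% | 10% vs 25% | 5.4% | 2.7% |
| 10% vs 25% | 10% vs 22.5% | 13.1% | 7.5% |
| 10% vs 25% | 10% vs 20% | 27.1% | 17.7% |

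The first three rows are power and the last three are false equivalence. With 100 per arm, 10 recurrences are expected in each arm, and a 5-point shift is five patients in one arm.

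**Feasibility of masking the patient.** Section 4.2 allows general or epidural anaesthesia without distinguishing the arms. Section 4.2.1.3 describes a transanal mucopexy repeated after six ligations in the Doppler arm and at six clock positions in the other arm. No excision is described. On that description a patient has little to tell the operations apart by. However, section 4.2 labels group B as Doppler-guided ligation without mucopexy, which conflicts with 3.1 and 4.2.1.3. The feasibility argument follows 3.1 and 4.2.1.3, and the passages must be reconciled.

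**The case against.** A reader might infer that the trial is open-label. The documents do not support this: the protocol is silent, and it nowhere says that patients are told their allocation. Section 9 lists a consent form and a form of words that are not in the text at hand and might address disclosure. The point therefore concerns the protocol body only.

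A reader might also infer that the primary endpoint is read directly from the questionnaires. Section 3.6 does not say so. The questionnaires and the recurrence definition are separate bullets, a control anoscopy is mentioned, and thrombosis could be seen on examination. The endpoint is symptom-based, and its link to the questionnaires is an inference. If an examiner who knows the allocation elicits the symptoms instead, the same route for bias is open.

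Several further objections stand in part.

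- Excluding patients with a clear preference reduces expectation bias at entry, and may have been meant for equipoise or adherence. It does not stop knowledge of the allocation from acting afterwards.
- The front matter already gives the Study Office the collection of data, so routing forms there may change little. It does not say who elicits the symptoms or whether that person is masked.
- Nothing says that the operating surgeon takes the questionnaires.
- The share of epidural anaesthesia is unknown, and an awake patient might notice the Doppler.
- The calculations show sensitivity to a shift from any cause. They do not show that missing masking would produce one, nor in which direction.

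**Conclusion.** The point holds in a limited form. The primary endpoint is defined by symptoms known mainly from the patient, and the protocol body specifies no masking of the patient or of whoever records recurrence. On the procedures as described in 3.1 and 4.2.1.3, masking the patient looks feasible.

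The possible effect is material against a 15-point limit. Under the assumed shifts, the chance of showing true equivalence falls by about 10 to 24 percentage points (93.8 − 83.7 and 93.8 − 69.3). False equivalence at the limit rises to between about two and five times its unbiased level (13.1/5.4 and 27.1/5.4). The pattern is the same at one-sided 0.025. These figures rest on the assumed size and direction of the reporting shift and on the assumed interval rule. They illustrate sensitivity and do not estimate bias in this trial. The change should be made, but its absence does not show that the trial's result would be wrong.

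**What to change.** In 3.1 and 3.3, state that patients are not told their allocation until the 1-year outcome has been recorded, and align the consent form. In 3.6, state that the symptom items defining recurrence are completed by the patient and returned to the existing Study Office before any unmasking, and are not elicited by the operating surgeon. Reconcile the description of group B in 4.2 with 3.1 and 4.2.1.3.

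This changes neither treatment nor sample size. It needs a few sentences, a consent revision and a routing rule for questionnaires that are already planned. The downsides are that disclosure is delayed to 1 year and that masking may be incomplete in patients awake under epidural anaesthesia.

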3.6.1 Definition of Adverse Events

- Urinary retention will be defined as the condition of urinary dysfunction that occurs following surgery and requires intervention, including placement of urinary catheter.
- Pyrexia will be defined as any documented patient temperatures >38.0 C that require any treatment intervention such as antipyretics or that result in an increase in hospital stay.
- Surgical site infection purulent discharge from the wound with positive culture
- Post operative bleeding requiring reintervention, or balloon tamponade of the anal mucosa or transfusion within 1 month from the operation

3.7 ELIGIBILITY CRITERIA

3.7.1 Inclusion Criteria

- Patients over 18 years old
- Symptomatic grade III hemorrhoids according to Goligher
- No other source of anal bleeding than hemorrhoids
- Written informed consent

3.7.2 Exclusion Criteria

- Any previous hemorrhoid surgery
- Participants expressing clear preference for one of the interventions
- Pregnancy
- Inability to understand the informed consent
- Oral anticoagulants of congenital defects of the coagulation
- Patients with immunodepression (i.e. HIV)
- Other proctological diseases (fissures, fistulas, condyloma, etc)
- IBD involving the anus ore the rectum

3.8 Withdrawal Criteria

Study participants will be informed of their ability to withdraw from the study or refuse initial enrollment at any time. Patients may withdraw without explanation.

4 STUDY INTERVENTION

4.1 Preoperative work-up

All the patients will have full proctological examination including anoscopy. Those with familiarity for colorectal cancer and those over 50 will be invited to have screening colonoscopy to exclude other sources of bleeding

4.2 Operative protocol

Patients with symptomatic grade III haemorrhoids will enter the study if they fulfil the entry and exclusion criteria and after written informed consent. They will be randomized in 2 groups: DGHAL with mucopexy (group A) and DGHAL without mucopexy (group B).

A cleansing enemas will be performed early in the morning at least 2 h before the operation. Antibiotic prophylaxis was not considered.

General or epidural anaesthesia will be performed according to the patient or anaesthetist preferences.

A urinary catheter will be inserted in all patients and removed after few hours from the operation.

The patients will be placed in the lithotomy position.

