Hamlet TRIAL

PROTOCOL

Full title: Multicenter randomized controlled trial of Doppler guided Hemorrhoid Artery Ligation (DGHAL) and mucopexy versus mucopexy alone in the treatment of grade III Hemorrhoids.

S

hort title: Hamlet (Hemorrhoids Artery Mucosal Ligation prospEctive Trial) trial.

Alternative title: Doppler-guided or non doppler-guided arterial ligation and mucopexy for third degree hemorrhoids? That is the question. The Hamlet (Hemorrhoids Artery Mucosal Ligation prospEctive Trial) trial.

Developed by Department of Emergency and Organ Transplantation (DETO), University of Bari,
Italy

Hamlet Trial Management Group

Surgery

[name], MD, [name]

Dept of Emergency and Organ Transplantation, University of Bari, Italy,
c/o Azienda Ospedaliero-Universitaria Policlinico di Bari, [name]
[contact] Mobile [contact]

[contact]

e-mail: [contact]

Randomization

Simple randomization will be centralized and carried out by assigning the 3 treatment options to consecutive computer generated random number obtained through the website http://www.randomizer.at

The randomization code will be obtained by contacting the number or the [contact]/ [name] or by the e-mail address [contact] or [contact].

Clinical queries during office hours should be directed to one of the clinical coordinators or to an appropriate member of the Hamlet Management Group

Data Monitoring and Ethics Committee

Clinical data monitoring will be carried out by [name]: Dept of Emergency and Organ transplantation, University of Bari e-mail: [contact] [contact]

Independent Ethics Committee of the Azienda Ospedaliero Universitaria Policlinico Consorziale Bari

[name]

[contact] [contact] e-mail: [contact]

Protocol approval n. 4555/2014

Trial Sponsor: University of Bari, Department of Emergency and Organ Transplantation, DETO,

Section of Surgery, Bari, Italy, [contact] - [name]

Clinicaltrial.gov ID number: Protocol version: 14/3/18

Hamlet Study Office

For general queries, supply of trial materials, and collection of data:

Trial Coordinator: [name], mobile [contact] – office [name] e-mail [contact]

Computing: [name], MD – mobile [contact] – e-mail: [contact]

CONTENTS

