2. STUDY HYPOTHESIS

The hypothesis of the study is that a simple mucopexy procedure by suture-fixation of anal cushion without the aim of a Doppler device, could be as effective as DGHAL and mucopexy to manage prolapsing grade III hemorrhoids.

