4.2.1.3 Mucopexy

After the haemorrhoid artery ligation, the suture is continued with three to five sutures applied 5 mm apart, making sure that the last is at least 5 mm above the dentate line. The suture is then tied to create a hemorrhoidopexy. The procedure is repeated after all artery ligations (6 ligations).

In the NON doppler group the mucopexy will start at two o'clock and repeated at 4, 6 8, 10, 12, in clockwise direction.

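### Section 4.2 defines group B as Doppler-guided ligation without mucopexy, the reverse of the arm described everywhere else in the protocol

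*Protocol*

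**What the plan says.** Protocol section 4.2 (Operative protocol) describes the two arms in one sentence: "They will be randomized in 2 groups: DGHAL with mucopexy (group A) and DGHAL without mucopexy (group B").

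Section 3.1 (General Design) says instead that patients are "randomized to either mucopexy without Doppler guided artery ligation or mucopexy with doppler guided hemorroidal artery ligation". The primary aim in section 3.2.1 is to show that "mucopexy without DGHAL for grade III haemorrhoids have equivalent recurrence rate at 1 year follow up of DGHAL with mucopexy procedure".

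Section 4.2.1.3, within the same operative section, describes mucopexy for both arms. For the Doppler arm: "After the haemorrhoid artery ligation, the suture is continued with three to five sutures applied 5 mm apart". For the other arm: "In the NON doppler group the mucopexy will start at two" o'clock, and it is repeated at 4, 6, 8, 10 and 12, which makes six positions.

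**The concern.** The trial combines two surgical components: Doppler-guided ligation and mucopexy. The design holds mucopexy constant and removes the ligation from one arm. The sentence in 4.2 holds the ligation constant and removes the mucopexy.

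Followed literally, that sentence gives group B a different operation. A surgeon could carry it out by performing the ligation in section 4.2.1.2 and stopping there. The trial would then estimate what mucopexy adds to DGHAL, and would not address whether Doppler-guided ligation can be left out, which is the question in sections 2 and 3.2.1. The instruction in 4.2.1.3 for a non-Doppler group would have no patients to apply to. Section 1.4 also credits the addition of mucopexy with extending DGHAL to third-degree disease, so the literal group B would omit that component in a grade III population.

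**Working it through.** No calculation is needed. The check sets every description of the arm beside the others.

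| Place in the protocol | Wording or content | Mucopexy? | Doppler-guided ligation? |
|---|---|---|---|
| Full title | "Doppler guided Hemorrhoid Artery Ligation (DGHAL) and mucopexy versus mucopexy alone" | yes | no |
| Alternative title | "Doppler-guided or non doppler-guided arterial ligation and mucopexy for third degree hemorrhoids" | yes | no |
| Section 2 | "a simple mucopexy procedure by suture-fixation of anal cushion without the aim of a Doppler device" | yes | no |
| Section 3.1 | mucopexy, no Doppler-guided ligation | yes | no |
| Section 3.2.1 | mucopexy, no DGHAL | yes | no |
| Section 4.2.1.3 | mucopexy at six clock positions in the non-Doppler group | yes | no |
| Section 4.2 | group B: DGHAL, no mucopexy | **no** | **yes** |

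1. **Count.** 6 + 1 = 7 descriptions. Six agree that the arm has mucopexy and no Doppler guidance; one, in 4.2, says the opposite on both components. The background remark in section 1.4 about mucopexy alone concerns earlier studies, so it is not counted.

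2. **The loosest of the six.** The alternative title can be read as allowing ligation without Doppler guidance, which is not quite mucopexy alone. It still gives mucopexy to both arms and Doppler guidance to only one, so it too conflicts with 4.2.

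3. **Arms given mucopexy.** Two of two in 4.2.1.3; one of two in the 4.2 sentence. Both statements cannot hold.

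4. **What each version compares.** Write D for Doppler-guided ligation and M for mucopexy. Intended: D+M against M, so the contrast isolates D. As written in 4.2: D+M against D, so the contrast isolates M.

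5. **Possible support for the 4.2 wording.** No other place describes an arm with DGHAL and no mucopexy. The randomization paragraph at the front of the protocol mentions three treatment options but does not name them. That is a separate inconsistency about the number of arms and does not support the 4.2 definition.

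6. **Effect on the figures.** Section 5.1 gives 100 per arm from power 0.8, type I error 0.05, an equivalence limit of 15% and 90% success in both groups. The group labels do not enter that calculation, so correcting the label leaves it as it stands.

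**The case against.** The strongest reply is that this is an editorial slip with little consequence. The hypothesis, design, primary aim and operative steps all state the right arm. A surgeon reading on from 4.2 soon reaches 4.2.1.3, which says what the non-Doppler group receives and where. The labels A and B are not used again in the protocol. Allocation is central and computer-generated (section 3.3), so 4.2 describes the groups but does not allocate anyone, and the protocol does not show what wording is issued with the randomization code. The tally of six against one includes two titles and does not measure seriousness.

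Most of this stands. The step from the sentence to a wrong operation is unproven, and the intended arm is recoverable. The conflict would rest securely on sections 2, 3.1, 3.2.1 and 4.2.1.3 even without the titles.

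It does not make the sentence harmless. The sentence defines an arm in the section surgeons operate from, and it is the only definition of A and B, so any form or listing using those labels could be traced only to the wrong text. Under section 3.5 the trial is open to surgeons across Europe, many of whom would work from the written protocol.

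**Conclusion.** The definition of group B in section 4.2 is wrong as written. One of seven descriptions of the arm is affected, and one of the two arm definitions in that sentence; group A is correct. The error is very probably a transposition. It changes no sample size, endpoint or analysis figure, and no misallocation is claimed because the protocol gives no basis for one. It should be fixed because it defines an arm, contradicts a subsection of its own section, and would change the trial's question if followed.

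The conclusion assumes that sections 2, 3.1, 3.2.1 and 4.2.1.3 express the intended design. Their agreement with each other and with both titles leaves no reasonable doubt of that.

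**What to change.** Amend the sentence in 4.2 so that the groups read: *DGHAL with mucopexy (group A) and mucopexy without DGHAL (group B)*. Notify all sites, and check that any form or randomization message using the labels A and B carries the corrected definition.

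The cost is a one-sentence correction and a notice. No extra patients are needed and the analysis does not change. Section 6.2 has the protocol approved by the ethics committee of every participating institution, so the correction may also need notification to those committees or their approval; the protocol does not say which.
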